2.3. Hypotheses

This is a feasibility study and all the hypotheses are exploratory in nature.

Primary Hypotheses:

There are two co-primary hypotheses in this study. Both of them must be met to satisfy the primary objective of the study.

1. The Test lens will be non-inferior to the Control lens with respect to logMAR visual performance (using ETDRS visual acuity charts) at the 2-week follow-up visit. A non-inferiority margin of 0.05 logMAR will be used.
2. The Test lens will be non-inferior to the Control lens with respect to average daily wear time at 2-week follow-up visit. A non-inferiority margin of 1 hour will be used.

Secondary Hypotheses:

1. The Test lens will be non-inferior to the Control lens with respect to overall CLUE comfort score at the follow-up visit. A non-inferiority margin of -5 points will be used.
2. The Test lens will be non-inferior to the Control lens with respect to overall CLUE vision score at the follow-up visit. A non-inferiority margin of -5 points will be used.

All primary hypotheses of this study have to be met for study success.

Clinical Study Protocol

Johnson & Johnson Vision Care, Inc.

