14.2. Sample Size Justification

The plan is to enroll 115 subjects with a target completion of 100 subjects with approximately 50 subjects in the Test group and approximately 50 in the Control group. This is a feasibility study, and the sample size is chosen not based on estimates from historical studies with the product characteristics. The data collected for this study will be used to design future clinical trials. Thus, power calculations were conducted under different scenarios for the primary hypotheses to provide estimates on power with 2-sided type I error of 0.05 given the parallel design and 1:1 randomization ratio for average daily wear time and LogMAR visual acuity test at a 4-meter distance under high luminance/low contrast (HLLC) and low luminance/high contrast (LLHC) conditions.

Table 7 provides a summary of power based on the hypothesis of non-inferiority for logMAR visual acuity test at a 4-meter distance under either HLLC or LLHC at 1 Week Follow-up visit with a non-inferiority margin of 0.05 logMAR. Table 8 provides a summary of power based on the hypothesis of non-inferiority for average daily wear time at 1-week follow-up visit with a non-inferiority margin of 1 hour. The power calculation based on two sample t-test is conducted using the POWER procedure in SAS 9.4.

Clinical Study Protocol

Johnson & Johnson Vision Care, Inc.

Table 7: Power Calculation for the first primary hypothesis of logMAR visual acuity for either HLLC or LLHC at 2-week follow-up with a non-inferiority margin of 0.05.

Mean Difference (Test - Control)	Type I error	Standard Deviation	Total Sample Size (n/2 per arm)	Power
-0.01	0.05	0.08	100	0.981
-0.01	0.05	0.09	100	0.952
-0.01	0.05	0.10	100	0.909
0.00	0.05	0.08	100	0.928
0.00	0.05	0.09	100	0.867
0.00	0.05	0.10	100	0.799

As shown in the Table 7, the power is 0.8 or higher to show non-inferiority of the Test relative to the Control with respect to logMAR VA test at a 4-meter distance under either HLLC or LLHC when the Test - Control ≤ 0 and the standard deviation for both Test and Control < 0.10 .

Table 8: Power Calculation for the second primary hypothesis of average daily wear time at 2-week follow-up with a non-inferiority margin of 1.

Mean Difference (Test - Control)	Type I error	Standard Deviation	Total Sample Size (n/2 per arm)	Power
-0.05	0.05	1.90	100	0.799
-0.05	0.05	1.93	100	0.788
0.00	0.05	1.90	100	0.834
0.00	0.05	1.93	100	0.823
0.05	0.05	1.90	100	0.864
0.05	0.05	1.93	100	0.855

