As shown in the Table 8, the power is 0.8 or higher to show non-inferiority of the Test relative to the Control with respect to when the Test - Control ≥ 0 and the standard deviation for both Test and Control ≤ 1.93 .

Clinical Study Protocol

Johnson & Johnson Vision Care, Inc.

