14.4. Level of Statistical Significance

Since this is a feasibility study, the primary and secondary endpoints will be each tested under a Type I error rate of 5%. If exploratory statistical analysis is conducted after reviewing the descriptive summary of an endpoint, a type I error rate of 5% will be used with no multiplicity adjustments.

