14.5. Primary Analysis

The co-primary endpoints for this study are the logMAR VA test at a 4-meter distance under either HLLC or LLHC and the average daily wear time at 2-week follow-up evaluated after 14 ± 4 days of lens wear. The primary analysis will be conducted on per-protocol populations.

Visual Performance

Monocular distance visual performance in logMAR scale at follow-up visits will be analyzed using a mixed model of repeated measurement (MMRM) for HLLC and LLHC respectively to compare between Test and Control lenses at 2-week follow-up. The model will include baseline logMAR, lens type, visit, and the interaction of lens type and visit as the fixed effect, and investigational site and patient as random effects. Baseline demographics such as age and gender have historically limited influence on objective visual performance; thus, in accordance with the principle of parsimony, will not be included in the model. The covariance of residual errors between two follow-up visits across periods for the same eye and subject across wearing periods will be modeled using an unstructured (UN) covariance structure.

The null and alternative hypotheses for non-inferiority of Test lens relative to Control are as follows:

$$H_0: \Delta > 0.05$$
$$H_A: \Delta \leq 0.05$$

Clinical Study Protocol

Johnson & Johnson Vision Care, Inc.

where Δ is the mean difference in logMAR between Test lens and Control lens (Test minus Control) at 2-week follow-up. Non-inferiority will be declared if the upper bound of the confidence interval of the mean difference between Test and Control is less than 0.05.

Average Daily Wearing Time

Average daily wear time will be analyzed using a similar MMRM model with fixed and random effects described in the primary analysis. Age and gender will also be included as fixed effects.

The null and alternative hypotheses for non-inferiority of Test lens relative to Control are as follows:

$$H_0: \Delta < -1$$
$$H_A: \Delta \geq -1$$

where Δ is the mean difference in average daily wearing time between Test lens and Control lens (Test minus Control) at 2-week follow-up. Non-inferiority will be declared if the lower bound of the confidence interval of the mean difference between Test and Control is greater than -1.

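### Section 14.2 gives power one test at a time, but study success needs both acuity and wear time; joint power at Test = Control is about 0.71 to 0.77 in the range claimed

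*Combined protocol and SAP*

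**What the plan says.** Section 2.3 names two co-primary hypotheses, non-inferior logMAR acuity (margin 0.05) and non-inferior average daily wear time (margin 1 hour), and ends: "All primary hypotheses of this study have to be met for study success".

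Section 14.2 plans for a "target completion of 100 subjects with approximately 50 subjects in the Test group and approximately 50 in the Control group". On method it says: "The power calculation based on two sample t-test is conducted using the POWER procedure in SAS 9.4". Table 7 covers acuity under either HLLC or LLHC, and Table 8 covers wear time. Each is followed by its own conclusion. For acuity, "the power is 0.8 or higher to show non-inferiority of the Test relative to the Control with respect to logMAR VA test", limited to a true difference of zero or below and an SD under 0.10. For wear time, "the power is 0.8 or higher to show non-inferiority of the Test relative to the Control", limited to a true difference of zero or above and an SD up to 1.93. No joint power is reported.

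On the error level, section 14.2 states a "2-sided type I error of 0.05", and section 14.4 says "the primary and secondary endpoints will be each tested under a Type I error rate of 5" percent, without giving sidedness. Section 14.5 gives no confidence level for the primary tests; section 14.6 uses a two-sided 95% interval for the secondary ones.

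On lighting conditions, section 2.2 evaluates acuity under both. Section 14.5 defines the endpoint as either one, and says acuity "will be analyzed using a mixed model of repeated measurement (MMRM) for HLLC and LLHC respectively". No rule for combining the two results is stated.

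**The concern.** When success requires every primary test to pass, the power that matters is the probability that all pass together. That cannot exceed the smallest single-test power and is usually lower. A reader of section 14.2 sees 0.8 or higher twice and may take 0.8 as the study's chance of success when the lenses do not differ. That case is central here, because the study asks whether a manufacturing change has any clinical effect. If the joint figure is lower, a failed study of equivalent lenses is more likely than the section suggests, and the sponsor should know this before interpreting a miss.

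**Working it through.** **Inputs.** From section 14.2: 50 completers per arm, a two-sample t-test, and the differences and SDs of Tables 7 and 8. From section 2.3: margins of 0.05 logMAR and 1 hour. The documents give no correlation between endpoints, so any correlation used below is an assumption.

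**Step 1: reproduce the tables.** Power is the probability that a noncentral t (98 df) exceeds the critical value. The noncentrality is (0.05 − Δ) / (SD × √(2/50)) for acuity and (1 + Δ) / (SD × √(2/50)) for wear time, with √(2/50) = 0.2.

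- Acuity, Δ = 0, SD 0.10: 0.05 / 0.02 = 2.5. One-sided 0.05 gives 0.799, as printed. One-sided 0.025, which is what two-sided 0.05 implies, gives 0.697.
- Wear time, Δ = 0, SD 1.93: 1 / 0.386 = 2.59. One-sided 0.05 gives 0.823, as printed. One-sided 0.025 gives 0.727.

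All 12 printed powers match to three decimals at one-sided 0.05. None comes within two percentage points at two-sided 0.05.

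**Step 2: both hypotheses, one acuity test, independent endpoints, Test = Control.** Joint power is the product of the two printed powers.

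| Acuity SD (power) | Wear-time SD 1.90 (0.834) | Wear-time SD 1.93 (0.823) |
|---|---|---|
| 0.08 (0.928) | 0.77 | 0.76 |
| 0.09 (0.867) | 0.72 | 0.71 |
| 0.10 (0.799) | 0.67 | 0.66 |

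The acuity sentence in section 14.2 excludes SD 0.10. Within the range it claims, joint power is therefore 0.71 to 0.77.

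**Step 3: all pairs in the claimed range.** Four acuity rows (Δ −0.01 or 0, SD 0.08 or 0.09) and four wear-time rows (Δ 0 or 0.05, SD 1.90 or 1.93) make 16 pairs. Seven reach 0.80:

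- acuity −0.01/0.08 with all four wear-time rows (0.808 to 0.848);
- acuity −0.01/0.09 with the two wear-time rows at 0.05 (0.814 and 0.823);
- acuity 0.00/0.08 with wear time 0.05/1.90 (0.802).

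Every one assumes a true advantage for Test on at least one endpoint.

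**Step 4: correlation between acuity and wear time.** At an assumed 0.5, the Test = Control range over all tabulated SDs is 0.70 to 0.80 (the best pair is 0.797). The bounds over any correlation are 0.622 to 0.799 for SDs 0.10/1.93 and 0.76 to 0.83 for SDs 0.08/1.90.

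**Step 5: the lighting-condition rule, Test = Control.**

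- If both conditions must pass, hypothesis 1 alone at SD 0.10 has power 0.638 (correlation 0) to 0.728 (correlation 0.8). At SD 0.09 it is 0.752 to 0.813, and at SD 0.08 it is 0.861 to 0.894. All three tests together, independent, give 0.799² × 0.823 = 0.53 up to 0.928² × 0.834 = 0.72.
- If one condition suffices, hypothesis 1 at SD 0.10 has power 1 − (1 − 0.799)² = 0.960 with independent tests, or 0.912 at correlation 0.5. Both are above the printed 0.799.

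**Step 6: the level the text states.** At two-sided 0.05, single-test power at Test = Control is 0.697 to 0.872 for acuity and 0.727 to 0.741 for wear time. The two-test product runs from 0.697 × 0.727 = 0.51 to 0.872 × 0.741 = 0.65.

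**The case against.** The sentences in section 14.2 are worded per endpoint, carry their own conditions, and are correct for one test at one-sided 0.05. The plan nowhere states a failure rate for the study as a whole. That stands: what is wrong is an omission, and no table entry is miscalculated.

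A reader might go further and infer that Table 7 overstates the power of hypothesis 1, since acuity is modelled under two lighting conditions. The documents do not support this. They speak of both conditions in one place and of either in others, and fitting a model to each is not a decision rule. If one condition is enough, Table 7 understates hypothesis 1. If both are needed, power still exceeds 0.8 at SD 0.08. For the same reason, 0.53 cannot be quoted as the study's power: it needs an unstated three-test rule, independence, and the SD that the text excludes.

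It can also be said that this is a feasibility study with exploratory hypotheses, that its size was not derived from historical estimates, and that future trials would be designed from its data rather than from these tables. This lowers the stakes. It does not remove the mismatch, because section 2.3 still sets a formal success rule.

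Finally, the planned mixed model uses repeated visits and covariates and may be more efficient than a t-test. That is possible, but section 14.2 quantifies no such gain.

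**Conclusion.** The point holds as an omission. Section 14.2 supports the sample size with single-test powers and never gives power for the rule in section 2.3. On the printed powers, with Test = Control, one acuity test and independent endpoints, the chance of meeting both hypotheses is 0.71 to 0.77 in the claimed range. Equivalent lenses would then miss the criterion 23% to 29% of the time, and 33% to 34% at acuity SD 0.10. A positive correlation between the endpoints narrows the gap.

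These figures rest on one-sided 0.05, which contradicts the level stated in the text. At the stated level the two-test figure is 0.51 to 0.65 over all tabulated SDs, and the per-test claim of 0.8 also fails: no wear-time row in the claimed range exceeds 0.781. No single joint figure can be called the right one until the level and the lighting-condition rule are fixed.

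**What to change.** In this order:

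1. Label Tables 7 and 8 as power for a single test.
2. State in sections 2.3 and 14.5 whether hypothesis 1 needs non-inferiority under both lighting conditions or under one.
3. Reconcile the two-sided 0.05 in section 14.2 with the one-sided 0.05 that the tables use, and state the confidence level for the primary tests in section 14.5.
4. Under that rule and level, add to section 14.2 the joint power for study success in each scenario, over a stated range of correlations between wear time and acuity and, if both lighting conditions count, between HLLC and LLHC.

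The cost is a short recalculation and a few reworded lines. No change in sample size is needed for a feasibility study. The downside is a less favourable stated power.

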14.3. Analysis Populations

Safety Population:

All subjects who are administered any test article excluding subjects who drop out prior to administering any test article. At least one observation should be recorded.

Per-Protocol Population:

All subjects who successfully complete all visits and do not substantially deviate from the protocol as determined by the trial cohort review committee prior to database hard lock. Justification for the exclusion of subjects with protocol deviations from the per-protocol population set will be documented in a memo to file.

Intent-to-Treat (ITT) Population:

All randomized subjects regardless of actual treatment and subsequent withdrawal from the study or deviation from the protocol. At least one observation should be recorded.

14.4. Level of Statistical Significance

Since this is a feasibility study, the primary and secondary endpoints will be each tested under a Type I error rate of 5%. If exploratory statistical analysis is conducted after reviewing the descriptive summary of an endpoint, a type I error rate of 5% will be used with no multiplicity adjustments.

14.5. Primary Analysis

The co-primary endpoints for this study are the logMAR VA test at a 4-meter distance under either HLLC or LLHC and the average daily wear time at 2-week follow-up evaluated after 14 ± 4 days of lens wear. The primary analysis will be conducted on per-protocol populations.

Visual Performance

Monocular distance visual performance in logMAR scale at follow-up visits will be analyzed using a mixed model of repeated measurement (MMRM) for HLLC and LLHC respectively to compare between Test and Control lenses at 2-week follow-up. The model will include baseline logMAR, lens type, visit, and the interaction of lens type and visit as the fixed effect, and investigational site and patient as random effects. Baseline demographics such as age and gender have historically limited influence on objective visual performance; thus, in accordance with the principle of parsimony, will not be included in the model. The covariance of residual errors between two follow-up visits across periods for the same eye and subject across wearing periods will be modeled using an unstructured (UN) covariance structure.

The null and alternative hypotheses for non-inferiority of Test lens relative to Control are as follows:

$$H_0: \Delta > 0.05$$
$$H_A: \Delta \leq 0.05$$

Clinical Study Protocol

Johnson & Johnson Vision Care, Inc.

where Δ is the mean difference in logMAR between Test lens and Control lens (Test minus Control) at 2-week follow-up. Non-inferiority will be declared if the upper bound of the confidence interval of the mean difference between Test and Control is less than 0.05.

Average Daily Wearing Time

Average daily wear time will be analyzed using a similar MMRM model with fixed and random effects described in the primary analysis. Age and gender will also be included as fixed effects.

The null and alternative hypotheses for non-inferiority of Test lens relative to Control are as follows:

$$H_0: \Delta < -1$$
$$H_A: \Delta \geq -1$$

where Δ is the mean difference in average daily wearing time between Test lens and Control lens (Test minus Control) at 2-week follow-up. Non-inferiority will be declared if the lower bound of the confidence interval of the mean difference between Test and Control is greater than -1.

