2.2. Endpoints

Primary Endpoint(s)

Average daily wear time (in hours):

Average daily wear time will be calculated as the number of hours between subjects reported time of insertion and time of removal of the study lenses, on an average day, at 2-Week Follow up evaluation.

Visual performance

Visual performance will be calculated as monocular contact lens-corrected distance visual acuity using a logMAR visual acuity scale. This will be evaluated under both high luminance/low contrast conditions and low luminance/high contrast conditions at 4 meters from Early Treatment Diabetic Retinopathy Study (ETDRS) charts at the 2 Week Follow-up visit.

Secondary Endpoint(s)

CLUE Comfort and Vision Scores:

The co-primary endpoints for this study are subjective assessment of comfort and quality of vision after 14 ± 4 days of wearing the study lenses as a daily disposable.

Subjective assessment of comfort and vision will be performed using the Contact Lens User Experience™ (CLUE) questionnaire.⁵ CLUE is a validated patient reported outcomes (PRO) questionnaire used to assess patient experience attributes of soft contact lenses (comfort, vision, handling, and packaging) in a US contact-lens wearing population between 18 and 65 years of age. CLUE composite scores are derived using Item Response Theory (IRT) and follow a normal distribution with a population average score of 60 (SD 20), where higher scores indicate a more favorable/positive response. A 5-point increase in an average CLUE score translates into 10% shift in the distribution of scores for the population of soft disposable contact lens wearers.

Other Endpoint(s)

Slit Lamp Findings

Frequency and severity by eye of slit lamp findings (SLFs) including conjunctival injection, corneal edema, corneal neovascularization, corneal staining, tarsal abnormalities or any other complications. SLFs will be evaluated at fitting and post-fitting evaluation visits including unscheduled visits.

Clinical Study Protocol

Johnson & Johnson Vision Care, Inc.

Subject's Reported Ocular Symptoms

Frequency and severity by eye of subject's reported ocular symptoms and problems with the study lens at fitting and post-fitting evaluation visits including unscheduled visits.

Lens Fitting characteristics

Frequency by eye of mechanical lens fitting characteristics including lens centration and lens movement and overall lens fitting acceptability at fitting and 2-week follow-up evaluations.

Lens wettability:

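### Section 14.5 does not say whether acuity must pass under one or both lighting conditions, or at what confidence level, and Tables 7 and 8 match one-sided 0.05, not the stated 2-sided 0.05

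*Combined protocol and SAP*

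**What the plan says.** Section 14.5 defines the co-primary endpoints as "the logMAR VA test at a 4-meter distance under either HLLC or LLHC and the average daily wear time at 2-week follow-up". Acuity is analysed "using a mixed model of repeated measurement (MMRM) for HLLC and LLHC respectively to compare between Test and Control lenses", which produces two treatment differences and two intervals. The decision rule is nevertheless singular: "Non-inferiority will be declared if the upper bound of the confidence interval of the mean difference between Test and Control is less than 0.05". The wear-time rule has the same form, and neither gives a confidence level.

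Other sections bear on the point without settling it:

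- Section 2.2 says of acuity: "This will be evaluated under both high luminance/low contrast conditions and low luminance/high contrast conditions at 4 meters".
- Section 2.3 states acuity as one hypothesis with no lighting condition named. It says "This is a feasibility study and all the hypotheses are exploratory in nature", but also "All primary hypotheses of this study have to be met for study success".
- Section 14.4 says "the primary and secondary endpoints will be each tested under a Type I error rate of 5" per cent, without sidedness.
- Section 14.2 describes its calculations as made "to provide estimates on power with 2-sided type I error of 0.05", using a two-sample t-test.
- Section 14.6 specifies a two-sided 95% interval, but only for the secondary CLUE scores.

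**The concern.** Two choices that decide the study verdict are open. If one lighting condition meets the margin and the other does not, section 14.5 read literally (either) gives success, while section 2.2 (both) gives failure. A result whose 90% interval clears the margin but whose 95% interval does not can likewise be called either way. If these choices are left until the data are unmasked, they can be made with the answer in view.

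The power statements are affected too. If the level printed in 14.2 is the one to be used, the tables overstate power. In addition, each table gives the power of a single test, whereas section 2.3 requires every primary hypothesis to be met. The chance of meeting the actual success rule is not shown.

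**Working it through.** **Inputs.** From 14.2: 50 completers per arm, 1:1 allocation, two-sample t-test, and the differences and SDs in Tables 7 and 8. From 2.3: margins of 0.05 logMAR and 1 hour.

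**Formula.** The noncentrality is e / (SD × √(2/50)) = e / (0.2 × SD). Here e = 0.05 − d for acuity and e = 1 + d for wear time, with d = Test − Control. Power is the probability that a noncentral t with 98 df exceeds the critical value: 1.661 at one-sided 0.05, or 1.984 at one-sided 0.025 (the lower or upper limit of a two-sided 95% interval).

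**Step 1: the plan's own figures.** For acuity with d = 0 and SD 0.10, 0.05 / (0.2 × 0.10) = 2.50. Power is 0.799 at one-sided 0.05 and 0.697 at one-sided 0.025. For wear time with d = 0 and SD 1.93, 1 / (0.2 × 1.93) = 2.591, giving 0.823 and 0.727. All rows:

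| Table | d | SD | Printed | One-sided 0.05 | One-sided 0.025 |
|---|---|---|---|---|---|
| 7 | −0.01 | 0.08 | 0.981 | 0.981 | 0.960 |
| 7 | −0.01 | 0.09 | 0.952 | 0.952 | 0.910 |
| 7 | −0.01 | 0.10 | 0.909 | 0.909 | 0.844 |
| 7 | 0 | 0.08 | 0.928 | 0.928 | 0.872 |
| 7 | 0 | 0.09 | 0.867 | 0.867 | 0.785 |
| 7 | 0 | 0.10 | 0.799 | 0.799 | 0.697 |
| 8 | −0.05 | 1.90 | 0.799 | 0.799 | 0.697 |
| 8 | −0.05 | 1.93 | 0.788 | 0.788 | 0.683 |
| 8 | 0 | 1.90 | 0.834 | 0.834 | 0.741 |
| 8 | 0 | 1.93 | 0.823 | 0.823 | 0.727 |
| 8 | 0.05 | 1.90 | 0.864 | 0.864 | 0.781 |
| 8 | 0.05 | 1.93 | 0.855 | 0.855 | 0.768 |

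All 12 printed values match one-sided 0.05, and none matches 2-sided 0.05. At the stated level, the sentence after Table 7 (difference ≤ 0, SD below 0.10) fails at d = 0, SD 0.09. The sentence after Table 8 (difference ≥ 0, SD up to 1.93) fails in all four rows it covers.

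**Step 2: which lighting rule the tables assume.** If passing under either condition sufficed, power at d = 0, SD 0.10, one-sided 0.05 would be 0.96 at an HLLC–LLHC correlation of 0 and 0.85 at 0.9. The printed 0.799 is therefore the power of one condition alone. It supports neither combining rule.

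**Step 3: type I error if one condition sufficed.** With both true differences at the margin, error = 2a − P(both reject), using a bivariate normal. The correlation is not in the documents; 0 to 0.9 is assumed.

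- a = 0.05: 0.10 − 0.0025 = 0.0975 (correlation 0), and 0.10 − 0.0319 = 0.0681 (0.9).
- a = 0.025: 0.05 − 0.0006 = 0.0494, and 0.05 − 0.0148 = 0.0352.

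Wear time must also pass. With its true difference 0, SD 1.93 h and independence, multiplying by 0.823 or 0.727 gives study-level error of 0.080 to 0.056, or 0.036 to 0.026.

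**Step 4: joint power if both conditions and wear time must pass.** At correlation 0 with SD 0.10 and 1.93 h: 0.799² × 0.823 = 0.525, and 0.697² × 0.727 = 0.353. Other correlations come from simulated correlated t pairs multiplied by wear-time power. Zero true differences, independent wear time, correlation 0 to 0.9:

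| SDs | One-sided 0.05 | One-sided 0.025 |
|---|---|---|
| 0.10, 1.93 h | 0.53–0.62 | 0.35–0.46 |
| 0.09, 1.90 h | 0.63–0.69 | 0.46–0.54 |
| 0.08, 1.90 h | 0.72–0.75 | 0.56–0.62 |

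**The case against.** The strongest reply is that this is a feasibility study with exploratory hypotheses, and that power did not set the sample size. The lighting rule is also arguably clear. Section 2.2 says both, 14.5 says respectively, and in the Table 7 title the word either naturally means whichever condition is being tested. On that reading only a sentence is missing, and the error rates in step 3 belong to the less likely interpretation. Section 14.4 links the 5% level to feasibility, so one-sided 0.05 may have been intended, leaving 2-sided in 14.2 as a slip.

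Much of this is fair, and it limits the stakes. The SD 0.10 row also lies just outside the 14.2 claim, so the acuity row that breaks that claim is SD 0.09. The study-level error in step 3 is one scenario and not a bound: as wear-time power approaches 1, it approaches the acuity-level figure. The joint-power line is useful but optional.

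What remains is that section 2.3 still defines success, and the word either sits in the primary analysis section itself. If 2-sided is a slip, it is the slip that decides between a 90% and a 95% interval.

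The planned model is not a simple t-test. Two eyes per subject, and baseline adjustment for wear time, could raise power. For acuity the baseline gain is uncertain, because Table 3 schedules ETDRS logMAR only at Visits 2 and 3. None of this affects the sidedness mismatch, which lies within the plan's own stated method.

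**Conclusion.** The concern holds, and it should be fixed. The sidedness contradiction is exact and needs no outside assumption. At the stated 2-sided 0.05 every row falls, by about 2 to 10 percentage points, wear-time power is 0.683 to 0.781 throughout, and both claims of at least 0.80 power fail on their own conditions. The missing confidence level is plain from 14.5 and cannot safely be inferred, since 14.2 and 14.6 point to 95% while the tables imply 90%.

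The lighting rule is an omission. The text leans towards testing both conditions, but nothing closes off the literal reading. The inflated error of 6.8 to 9.75% (or 3.5 to 4.9% at per-test 2.5%) arises only if one condition suffices and both true differences sit at the margin. It disappears at correlation 1. The joint-power figures rest on the assumed correlation range, independent wear time and the plan's t-test.

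**What to change.** 1. **Lighting rule.** In 14.5 replace the either/or wording with both HLLC and LLHC. In 14.2 and the Table 7 title refer to each of the two conditions. Add to hypothesis 1 in 2.3 that it is met only if non-inferiority at 0.05 logMAR is shown under both conditions at the 2-week visit. If one condition is meant to suffice, name it in advance or split the alpha.
2. **Confidence level.** State it in 14.5 for both primary decisions. Two-sided 95% agrees with 14.2 and 14.6. If 90% is intended, correct the sidedness in 14.2 and explain the difference from 14.6.
3. **Power.** Present Tables 7 and 8 and the sentences after them at the chosen level. Preferably add one line giving the joint power of the three tests, with its correlation assumptions.

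The cost is wording in 2.3, 14.2 and 14.5 and, at 95%, two restated tables. The price of choosing 95% is a less favourable power statement, with no wear-time row at 0.80. Requiring all three tests to pass needs no alpha adjustment, and no change in sample size is asked for.
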